4.5.8.3. Clinic Visits – M3, M6, M9, M12/EOT

- ECOG Performance Status
- Haematology - FBE
- Biochemistry – Renal function tests (Electrolytes and creatinine) and liver function tests (includes Bilirubin, ALT and ALP)
- Ig levels (trough if on 4-weekly IVIg, steady-state if on SC Ig)
- Concomitant medications: Treatment for underlying haematological malignancy, other immunosuppressive therapies (including steroids) for any indication, and non-trial antibiotic, antifungal and antiviral use and vaccinations. See site manual and eCRF for further details.
- Safety monitoring
- Infectious event details (including review of patient diary entries)
- Compliance with therapy
- Quality of life assessment (EQ-5D-5L, EORTC QLQ-C30 & FACT-N)
- Biobank sub-study only

- Peripheral blood (whole blood and serum) for correlative studies, including COVID-19 anti-spike protein levels (Month 3, Month 6, Month 9 and Month 12 only. Not required at EOT unless the EOT visit coincides with Month 12)
- Faecal sample (Month 3 and Month 12/EOT only)

If for any reason it is not considered in the participant's best interests to attend the trial site for an in-clinic assessment (as per local Investigator discretion), this Protocol allows for tele-health appointments to be conducted instead of on-site visits. Any such decisions are to be documented in the participant's source notes.

4.5.8.4. *Monthly phone calls – M1, M2, M4, M5, M7, M8, M10, M11*

- Concomitant medications: Treatment for underlying haematological malignancy, other immunosuppressive therapies (including steroids) for any indication, vaccines and non-trial antibiotic, antifungal and antiviral use. See site manual and eCRF for further details.
- Safety monitoring
- Infectious event details (including review of patient diary entries)
- Compliance with therapy

4.6. OUTCOME ADJUDICATION COMMITTEE (OAC)

An independent outcome adjudication committee, comprising of infectious disease experts and haematologists, will be established. The OAC will be responsible for reviewing and adjudicating on: grade of all infection outcomes, time of major infections; clinically documented infections; microbiologically documented infection; susceptibility profile of microbiologically documented infections and infection-related mortality.

The OAC will be provided with the details of all infectious events. Details will be provided in a blinded fashion, to ensure that the OAC are not aware of which treatment arm the participant was receiving. Committee members will individually assess the events according to the secondary outcomes as outlined above. All members will subsequently participate in a series of teleconferences for final consensus decision on the primary and secondary end-points for each trial patient.

5. Statistical Methods

Summary statistics, analyses and data visualisations will be generated using R version 4.0.0 or later or documented procedures in SAS (9.4 or later) or Stata (V. 17 or later) as appropriate. A detailed

description of the trial estimands, approaches to reporting, statistical models, adaptations and decision criteria, and justification of the trial design by simulation are presented in the Master Statistical Analysis Appendix to the Core Protocol and the Domain-specific Statistical Analysis Plans (SAPs). A Simulations Appendix will be updated periodically as an operational document which will contain the results of Monte Carlo simulations that are conducted to demonstrate and understand the operating characteristics of a domain or comparison of interest, across a range of plausible assumptions regarding the outcome rates, treatment effects, and recruitment rates.

The RATIONAL-PT has an adaptive platform design which means that it does not have a fixed sample size that determines when the study will end. Individual domains may have fixed caps on sample size as described within their DSAs.

The primary analysis will be a standalone analysis of each comparison within each domain of the RATIONAL-PT.

Interim analyses will be conducted according to the schedules specified in the relevant domain-specific appendices/SAPs and DSMC Charter, which will be reviewed and approved by the DSMC. The adaptations that can be made may be domain-specific and will be conducted according to pre-specified rules that will be used to reach conclusions regarding the effectiveness of the interventions that are under investigation. These may include: declaration of proof-of-concept, early stopping of arms for futility, early stopping of arms for efficacy and response adaptive randomisation (RAR). The values for the thresholds for the adaptations will be domain-specific and will take into account the design and monitoring plan for the domain. These will be appraised and ratified by the ITSC prior to the first interim analysis being conducted. The results of the interim analyses will remain confidential unless a trigger has been met and a recommendation is made by the DSMC to the ITSC that a conclusion has been reached and that they should be unblinded.

Blinding and randomisation: If domain-specific RAR is not invoked, computer-generated, randomised, allocation sequences will be based on permuted blocks of variable size; fixed allocation proportions will be adopted in the randomization of patients to the treatment arms in the domain and randomisation will be stratified by haematological malignancy.

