2. INTRODUCTION

2.1. Background and rationale

2.1.1. Overview

2.1.1.1. Infections in patients with blood cancers

Serious or major infection is common in patients with chronic lymphocytic leukaemia (CLL), multiple myeloma (MM) and non-Hodgkin lymphoma (NHL). These blood cancers are associated with major morbidity and mortality, substantial impact on patient quality of life (QoL), and high health resource use and costs. Infections occur secondary to a multifactorial immune deficiency attributable to both the underlying cancer and/or its treatment.¹⁻⁴ Hypogammaglobulinaemia occurs in up to 85% of people with CLL, >90% newly diagnosed MM and variably in NHL, and is associated with recurrent and/or severe bacterial, fungal & viral infections.^{3,5,6} Infections account for up to 50% of all CLL deaths, and 50% of early MM deaths.^{5,7} When serious infections occur, they are complex and costly to manage, and impair cancer treatment delivery by causing dose reductions or treatment delays. Prevalence and severity of immune deficiency generally correlates with disease stage and duration; however infectious risk prediction for individual patients remains difficult. Identifying interventions to prevent infection is therefore a priority to improve infectious outcomes, survival and QoL of patients living with these cancers.

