6.2. Adverse event reporting

6.2.1. All Adverse Events (AEs)

All AEs that occur between the first trial-related procedure (i.e. screening) and 30 days following end of domain intervention must be recorded on the AE log.

Investigators must record their opinion concerning details of the nature, onset, duration and severity of the AE, and assess any relationship to the trial intervention. Assessment criteria are defined below. **Severity**

Severity for each adverse event, including any lab abnormality, will be determined by the Investigator using the Common Terminology Criteria for Adverse Events v5.0 (CTCAE) as a guideline, wherever possible. In those cases where the CTCAE criteria do not apply and where there is no accepted alternative grading system, severity should be defined according to the following criteria:

Mild	Awareness of sign or symptom, but easily tolerated
Moderate	Discomfort enough to cause interference with normal daily activities
Severe	Inability to perform normal daily activities

Life-threatening Immediate risk of death from the reaction as it occurred.

Causality

Relationship to trial treatment will be determined by the Investigator as follows:

Unrelated	No relationship between the experience and the administration of the trial treatment; related to other aetiologies such as concomitant medications or participant's clinical state
Unlikely	The current state of knowledge indicates that the relationship is unlikely
Possibly related	Temporal association, but other aetiologies are likely to be the cause
Probably related	Temporal association, other aetiologies are possible but unlikely
Related	Established temporal or other association and event not reasonably explained by the participant's known clinical state or other modes of therapy administered

Expectedness

An expectedness assessment needs to be conducted for all SAEs by the Sponsor with regard to the trial intervention, using the appropriate investigator brochure or treatment information.

Expected	The event is listed in the investigator brochure or the trial protocol as expected with the trial treatment or is commonly seen in clinical experience (patient population, dosage).
Unexpected	The event is not listed in the investigator brochure or in the trial protocol, or the severity of the event is greater than that listed in the investigator brochure or the trial protocol.

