6.3.2. Death

All deaths occurring on trial must be reported as an outcome on the SAE form and on the eCRFs. For all deaths, available autopsy reports (or death certificate if available) should be sent with the notification.

NB: Death is the outcome of a SAE; it cannot be the AE term unless no other information is available.

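### Section 4.6 asks the blinded committee to adjudicate infection-related mortality but does not state that a death with no site-recorded infectious event reaches it

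*Protocol*

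**What the plan says.** Protocol section 4.6 sets out both what the OAC decides and what it is sent.

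- **Remit.** The list of matters to adjudicate ends with "susceptibility profile of microbiologically documented infections and infection-related mortality". The section closes with teleconferences that reach a "final consensus decision on the primary and secondary end-points for each trial patient".
- **Input.** "The OAC will be provided with the details of all infectious events". The details are masked as to treatment arm. No other material is named.

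Deaths are handled elsewhere. Section 6.3.2 states: "All deaths occurring on trial must be reported as an outcome on the SAE form and on the eCRFs". It adds that "available autopsy reports (or death certificate if available) should be sent with the notification". Under section 6.3, SAE reports go to the sponsor's coordinating unit. Under section 6.3.4, the Chief Investigator or a medically qualified delegate reviews all adverse events, and listings go to the DSMC. Neither section mentions the OAC.

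On who classifies an event, section 6.2.1 states: "Investigators must record their opinion concerning details of the nature, onset, duration and severity of the AE". Section 6.3.2 notes: "Death is the outcome of a SAE; it cannot be the AE term unless no other information is available". Section 4.5.4 makes open-label treatment the default, which a Domain-Specific Appendix may change.

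**The concern.** Whether a death was infection-related is the question the OAC is there to answer without knowing the arm. If its file contains only events already recorded as infectious, an investigator who usually knows the allocation has partly answered that question first. Review then works in one direction for part of the deaths. The committee can reject a site's attribution to infection, but where the site recorded no infection it is given nothing from which to make one.

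At stake is infection-related mortality at 12 months. If sites in one arm were readier to ascribe a death to the malignancy than to infection, the adjudicated comparison would carry that difference. Blinded adjudication could not correct it, because it would never see those deaths.

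**Working it through.** The Protocol has no figure to reproduce on this point, so the check traces each kind of death through the text.

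**Step 1: which deaths have a stated route to the OAC?**

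| How the site recorded the case | Stated route to the OAC | What the OAC can do |
|---|---|---|
| Fatal event entered as an infection | Yes, as an infectious event (4.6) | Accept or reject infection as the cause |
| Fatal event entered under another term, infection also recorded | Yes, through the recorded infection (4.6) | Consider whether the infection led to death |
| Fatal event entered under another term, no infection recorded | None stated | Nothing from which to find infection as the cause |

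Only the third row is a gap.

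**Step 2: is another route stated?** Section 6.3.2 sends deaths to the SAE form and eCRFs. Section 6.3 sends SAE reports to the coordinating unit, and section 6.3.4 sends listings to the DSMC. Section 2.3.1 mentions the OAC only as a body with which the steering committee liaises. Section 2.3.5 names a charter for the DSMC; the Protocol names none for the OAC.

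**Step 3: what keeps the third row small?**

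- Infections and hospitalisations are reviewed at every visit (section 1.2). Infection details, including diary entries, are collected at clinic visits and monthly calls (sections 4.5.8.3 and 4.5.8.4).
- Serious infections stay under 24-hour reporting even though other disease-related SAEs are exempt (section 6.3.1).
- Follow-up SAE reports must include laboratory findings and hospital reports (section 6.3).
- All adverse events have a central medical review (section 6.3.4). The section does not say that this reviewer is blinded to allocation, or that a case may be passed on to the OAC.
- Because death is not normally the event term, the site must name the underlying event. This often helps: a terminal pneumonia would be entered as an infection.

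**Step 4: which outcomes depend on it?** EFS (section 3.2.1) counts death from any cause, so the death is an event whatever its cause. All-cause mortality (secondary outcome 6) does not use cause either. Infection-related mortality (secondary outcome 7) does.

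**Step 5: can the bias be sized?** Suppose the OAC judges correctly every death it sees. Let r1 and r0 be the proportions, in the two arms, of truly infection-related deaths that have a recorded infectious event. Then

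adjudicated ratio = true ratio × (r1 / r0).

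If r1 = r0 the ratio is not shifted, although the counts in both arms are too low when the common value is below 1. The Protocol gives neither r1 nor r0, nor a number of deaths, so no value follows. If all deaths are sent, r1 = r0 = 1 and this component disappears.

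**The case against.** The strongest reply is that the point rests on silence. Section 4.6 does not say that infectious events are all the committee receives. Adjudication files are commonly specified in a charter or manual, and the site manual, eCRF and Domain-Specific Appendices are not shown. They may hold a route for deaths. That stands as a limit: the finding is that the Protocol does not state a route, not that none exists. It does not dispose of the point, because section 4.6 itself fixes both the remit and the input, and the two should agree.

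A second reply is that a committee deciding every end-point for each patient must know who died. That is a fair inference about the fact of death. It widens what the committee decides, but not the material it is given on cause.

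A third reply is that several safeguards already catch fatal infections. This is correct and limits the point to deaths with no infectious event recorded.

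A reader might also infer more than the text supports:

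- **That every death filed under another cause escapes review.** It does not if an infection was recorded for that patient.
- **That the size can be read from the background section**, which states: "Infections account for up to 50% of all CLL deaths, and 50% of early MM deaths". These figures describe CLL deaths and early myeloma deaths, with none given for NHL. Participants here are selected for low IgG, or for reduced IgG with recurrent or severe infection. The figures neither cap nor estimate the infection share in this trial, and they say nothing about differences between arms.
- **That the primary result is undermined.** Death counts in EFS regardless of cause. Capture of non-fatal infections is a separate matter, covered by review at every visit, and nothing in the Protocol shows it to be deficient.

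**Conclusion.** The point holds in a limited form. As written, section 4.6 makes the OAC responsible for infection-related mortality without stating that it sees deaths for which the open-label site recorded no infectious event. The exposure is confined to secondary outcome 7. The text permits a difference between arms in how deaths are attributed, but does not show one, and no size of bias can be derived. The conclusion assumes that the committee's file follows section 4.6 as written and that the default open-label arrangement applies in the domain. This is a cheap improvement worth making, not a flaw in the primary analysis.

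**What to change.** Replace the input sentence in section 4.6 with wording such as: *The OAC will receive, with treatment allocation removed, the record of every infectious event and of every death, whatever cause the site assigned, together with any autopsy report or death certificate available.*

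The committee already exists, and section 6.3.2 already requests these documents for all deaths. The cost is the extra death dossiers to mask and review. Masking needs care, since the SAE report carries an assessment of relatedness to the assigned intervention. The number of dossiers cannot be calculated, because the Protocol gives neither the expected number of deaths nor the share that would already have been sent as infectious events. The change removes the site's control over which deaths are reviewed; it does not remove any influence of the site's narrative within a dossier. It is best made before deaths accrue, since a later change of referral rule is harder to defend.

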6. SAFETY ASSESSMENT

6.1. Definitions of adverse events

6.1.1. Adverse Event (AE)

Any untoward medical occurrence in a patient or clinical trial participant administered a medicinal product and that does not necessarily have a causal relationship with this treatment.

6.1.2. Adverse Reaction (AR)

Any untoward and unintended response to an investigational medicinal product related to any dose administered. All adverse events judged by either the reporting investigator or the sponsor as having a reasonable possibility of a causal relationship to an investigational medicinal product would qualify as adverse reactions. A causal relationship between the trial treatment (or medication error, misuse/abuse of medicinal product) and an adverse event occurs where there is at least a reasonable possibility that the trial treatment caused the event, i.e. the relationship cannot be ruled out.

6.1.3. Serious Adverse Event (SAE) / Serious Adverse Reaction (SAR)

Any adverse event/adverse reaction, at any dose, that

- Results in death
 - Is life-threatening (NB: 'life-threatening' refers to an event in which the participant was at risk of death at the time of the event. It does not refer to an event that hypothetically might have caused death if it were more severe.)
- Results in persistent or significant disability/incapacity
- Requires in-patient hospitalisation or prolongs existing hospitalisation
- Results in congenital anomaly or birth defect
- Is otherwise medically significant (i.e. all accidental or intentional overdoses whether they result in an adverse event or not, or any event which the investigator considers significant but which is not covered by the above)

Planned hospitalisations for a pre-existing condition, without serious deterioration in health, is not considered a serious adverse event.

6.1.4. Unexpected Adverse Reaction (UAR)

This is defined as an adverse reaction, the nature or severity of which is not consistent with the trial's reference safety information (i.e. current Investigator's Brochure or Product Information).

6.1.5. Suspected Unexpected Serious Adverse Reaction (SUSAR)

An adverse reaction to one or more of the interventions administered in this study, that is both serious and unexpected.

A serious event or reaction is not defined as a SUSAR when:

- it is serious but expected
- it does not fit the definition of an SAE, whether expected or not

6.1.6. Significant Safety Issues (SSIs) and Urgent Safety Measures (USMs)

An SSI is defined as a safety issue that could adversely affect the safety of participants or materially impact on the continued ethical acceptability or conduct of the trial. An example of an SSI is an SAE associated with trial procedures that requires modification to trial conduct.

An USM is a measure required to be taken in order to eliminate an immediate hazard to a participant's health and safety. An USM is a type of SSI that requires the Investigator or Sponsor to act immediately to protect the participant. For this reason, USMs can be instigated by an Investigator or Sponsor before seeking approval from HRECs or Institutions.

All Urgent Safety Measures instigated at the site must be reported to Monash University as soon as possible and within 24 hours of the measure being taken.

6.2. Adverse event reporting

6.2.1. All Adverse Events (AEs)

All AEs that occur between the first trial-related procedure (i.e. screening) and 30 days following end of domain intervention must be recorded on the AE log.

Investigators must record their opinion concerning details of the nature, onset, duration and severity of the AE, and assess any relationship to the trial intervention. Assessment criteria are defined below. **Severity**

Severity for each adverse event, including any lab abnormality, will be determined by the Investigator using the Common Terminology Criteria for Adverse Events v5.0 (CTCAE) as a guideline, wherever possible. In those cases where the CTCAE criteria do not apply and where there is no accepted alternative grading system, severity should be defined according to the following criteria:

Mild	Awareness of sign or symptom, but easily tolerated
Moderate	Discomfort enough to cause interference with normal daily activities
Severe	Inability to perform normal daily activities

Life-threatening Immediate risk of death from the reaction as it occurred.

Causality

Relationship to trial treatment will be determined by the Investigator as follows:

Unrelated	No relationship between the experience and the administration of the trial treatment; related to other aetiologies such as concomitant medications or participant's clinical state
Unlikely	The current state of knowledge indicates that the relationship is unlikely
Possibly related	Temporal association, but other aetiologies are likely to be the cause
Probably related	Temporal association, other aetiologies are possible but unlikely
Related	Established temporal or other association and event not reasonably explained by the participant's known clinical state or other modes of therapy administered

Expectedness

An expectedness assessment needs to be conducted for all SAEs by the Sponsor with regard to the trial intervention, using the appropriate investigator brochure or treatment information.

Expected	The event is listed in the investigator brochure or the trial protocol as expected with the trial treatment or is commonly seen in clinical experience (patient population, dosage).
Unexpected	The event is not listed in the investigator brochure or in the trial protocol, or the severity of the event is greater than that listed in the investigator brochure or the trial protocol.

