6.3.1. Adverse Events that require expedited reporting (within 24 hours)

Any SAEs or SARs or unexpected (but not serious) adverse reactions (UARs) must be reported to Monash University within 24 hours of the investigator becoming aware of the event, unless these have been specifically excluded from expedited reporting. These are SAEs that are associated with the participant's underlying disease, and will not impact on the scientific interpretation of the results of the trial.

Due to the seriousness of the underlying diseases from which the participants in this trial are suffering, the following situations that fulfil the definition of an SAE are excluded from expedited notification, but should be recorded on the SAE form and reported within 5 working days:

- Hospitalisation for pre-existing conditions that, in the investigator's opinion, have not been exacerbated by trial intervention
- Any other serious event related to the underlying disease or other medications used to treat the disease. Serious infections are not excluded from expedited notification.

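### The expectedness table in Section 6.2.1 overlaps itself and departs from Section 6.1.4, so one serious related reaction can be both a SUSAR and not a SUSAR

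*Protocol*

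**What the plan says.** Four parts of the Protocol bear on expectedness.

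- **Section 6.1.4** defines an unexpected adverse reaction as one "the nature or severity of which is not consistent with" the trial's reference safety information. It gives the current Investigator's "Brochure or Product Information" as that reference.
- **Section 6.1.5** makes a reaction that is serious and unexpected a SUSAR, and excludes a reaction when "it is serious but expected".
- **Section 6.2.1, lead-in to Expectedness**, has the sponsor assess every SAE "using the appropriate investigator brochure or treatment information".
- **Section 6.2.1, table.** The Expected row has two alternatives: the event is listed in the brochure or the trial protocol, "or is commonly seen in clinical experience (patient population, dosage"). The Unexpected row also has two. One turns on listing alone: "The event is not listed in the investigator brochure or in the trial protocol". The other brings in a severity test: "or the severity of the event is greater than that listed in the investigator brochure or the trial protocol".

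SUSAR status then drives the investigator's report to the institution (Section 6.3.3) and, where required, the sponsor's report of Australian SUSARs to the regulator (Section 6.3.4).

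**The concern.** The two rows ought to be complementary, and they are not. The second alternative in the Expected row needs no listing, while the Unexpected row is met by absence from the list alone. Nothing says which row prevails. A serious related reaction that is common in practice but unlisted can therefore be reported as a SUSAR by one assessor and set aside as expected by another.

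The case is plausible in this trial. The parenthesis in the Expected row refers to the patient population, and Section 2.1.1.1 describes serious infection as common in CLL, MM and NHL. Section 6.1.2 counts an event as an adverse reaction when a causal link cannot be ruled out, and Section 6.2.1 allows a rating of possibly related even when other causes are likely. An unlisted serious infection rated possibly related could thus be called expected because of its background frequency alone.

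More than one person may apply the table. Section 6.2.1 gives the assessment to the sponsor, Section 6.3 also requires expectedness in the initial SAE report, and Section 6.3.3 makes the investigator responsible for reporting SUSARs to the institution.

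**Working it through.** No arithmetic on trial figures applies. The check treats the table as logical rules and compares the result with Section 6.1.4.

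Let L = listed in the brochure or protocol, C = commonly seen in clinical experience, and S = more severe than listed (which has meaning only if L holds).

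- Expected (6.2.1) = L or C
- Unexpected (6.2.1) = (not L) or S
- Unexpected (6.1.4) = nature or severity not consistent with the reference safety information

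| Case | L | C | S | Row(s) met in 6.2.1 | 6.1.4* |
|---|---|---|---|---|---|
| 1 | yes | no | no | Expected | expected |
| 2 | yes | yes | no | Expected | expected |
| 3 | yes | no | yes | **both** | unexpected |
| 4 | yes | yes | yes | **both** | unexpected |
| 5 | no | yes | – | **both** | unexpected |
| 6 | no | no | – | Unexpected | unexpected |

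*Assuming that listed means listed in the reference safety information of Section 6.1.4, and not listed means absent from it.

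The rows overlap in 3 of the 6 cases, and in those same 3 the Expected row contradicts Section 6.1.4. The overlaps arise in two ways:

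1. **Unlisted but commonly seen (case 5).** The second Expected alternative and the first Unexpected alternative both hold. For a serious related reaction, Section 6.1.5 gives a SUSAR by the Unexpected row and by 6.1.4, but not by the Expected row.
2. **Listed but more severe than listed (cases 3 and 4).** The Expected row carries no severity condition, so its first alternative holds together with the second Unexpected alternative. Section 6.1.4 would settle this as unexpected, but the table does not refer to it.

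The reference documents, side by side:

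| Place | Documents named |
|---|---|
| 6.1.4 | Investigator's Brochure or Product Information |
| 6.2.1 lead-in | brochure or treatment information |
| 6.2.1 rows | brochure or trial protocol |

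The mismatch can change the answer. An event found only in the Product Information is unlisted under the table but can be expected under 6.1.4. An event listed only in the trial protocol is expected under the table but unexpected under 6.1.4.

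Testing the remedy: deleting the clause on clinical experience turns case 5 into Unexpected only, but leaves cases 3 and 4 in both rows. If Expected means that nature **and** severity are consistent with one named reference, and Unexpected means otherwise, the rows are complements and no overlap remains.

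**The case against.** The strongest reply is that the Protocol already leans one way. Section 6.1.4 is the formal definition, Section 6.1.5 builds on the same term, and the 6.2.1 lead-in points the sponsor to documents. One loose clause departs from this. That is fair, and it makes the defect an ambiguity rather than a gap. But the lead-in neither cancels the clause nor ranks the rows, and the table is what an assessor will use.

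The severity overlap can be called a strained reading, since the Unexpected row plainly presupposes a listed event. It is indeed the weaker of the two and rests on a literal reading. Likewise, treatment information may be loose wording for Product Information; even so, the table rows omit Product Information.

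The 24-hour rule in Section 6.3.1, under which "unexpected (but not serious) adverse reactions (UARs) must be reported to Monash University within 24 hours", also turns on the word unexpected, as does the reporting of reactions to trial antibiotics in Section 6.3.5.2. The expectedness assessment is stated for SAEs only, so the ambiguity carries over there only if sites apply the same table to non-serious reactions. Section 6.2.1 is headed as covering all adverse events, so the text does not exclude that.

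The safeguards are real. Serious reactions go to the sponsor within 24 hours whether expected or not, apart from the stated exclusions (6.3.1). The DSMC receives event listings (6.3.4). Sponsors must report events that meet the regulator's criteria (6.3.5.1). Suspected reactions to Ig go to the transfusion service and haemovigilance with no expectedness test (6.3.5.2). These routes limit the harm, but they do not settle whether an event is a SUSAR under this Protocol.

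**Conclusion.** The point holds: the table is wrong as written and should be fixed. In the text there are two ways an event can meet both rows and three different pairs of reference documents for one concept. The first overlap, the unlisted but commonly seen reaction, is certain from the wording; the second depends on reading the Expected row literally.

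The Protocol gives no basis for estimating how often such events would occur, and the net effect on the number of SUSARs is unknown. The consequence is confined to safety classification and the reporting tied to it. No endpoint or efficacy analysis is touched. The domain and regional appendices were not available; they may name a reference document for each intervention, but the conflict lies within the core Protocol text.

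**What to change.** In Section 6.2.1:

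- Delete the clause on clinical experience from the Expected row.
- Define Expected as consistent in both nature and severity with the reference safety information named for that intervention (the current Investigator's Brochure or Product Information, as in Section 6.1.4), and Unexpected as everything else.
- Use that same term in the lead-in in place of treatment information.
- If listing in the trial protocol or a domain appendix is meant to count, add it to Section 6.1.4 as well, so that both sections share one reference.

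All three wording changes to the table and lead-in are needed: the deletion removes only the first overlap, the severity condition removes the second, and the single reference removes the source mismatch. The cost is Protocol wording, plus naming the reference safety information for each intervention where a domain appendix does not already do so. Because the core Protocol governs every domain, one correction serves them all.
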